#### **10.5.3 Co-administration of SSRIs and Celecoxib**

Safety data from co-administration of a SSRI and celecoxib is available from a handful of studies (7, 41-43) using various dose regimens over period of times similar to the present study. All of these studies support a cardiovascular and gastrointestinal profile not different to the placebo treatments, but significant limitations arise from i) the small sample sizes, up to n=20 per group, ii) the patients selected for the study, these belong to different groups at risk, i.e. age, e.g. 24-46 years of age (41), and gender, i.e. only premenopausal women (43), and iii) the method of assessing cardiovascular and gastrointestinal adverse events, e.g. "checklist administered by a resident" as stated in (41).

**Both escitalopram and celecoxib are weak inhibitors of CYP2D4. Increases in the area under plasma drug concentration over time curve (AUC) can be expected between  $\geq 1.25$  but  $< 2$ -fold (44). Drug clearance may decrease by 20-50% (44). To retrospectively attribute adverse events to differences in drug exposure, plasma samples will be collected for pharmacokinetic analysis at select time points.**

#### **10.5.1 Gastrointestinal Bleeding Risk of Celecoxib**

NSAIDs, including Celecoxib, cause an increased risk of gastrointestinal adverse events including bleeding, ulceration, and perforation of the stomach or intestines. These events can be fatal. Patients with a current diagnosis of peptic ulcer disease and/or gastrointestinal bleeding will therefore be excluded. GI/bleeding risk will be screened for in medical history & physical examination. In weekly intervals, each patient will be monitored for GI pain and GI bleeds. In addition, hepatic function panel and hematocrit blood testing before entering the study, during week 1 or 2, and at the end of the study will screen for the presence of blood in stool and loss of excessive blood.

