## 5.2 Recruitment, screening and baseline assessments

Brief Summary of Procedures (also see attached schedule of procedures and assessments):

Potential participants will be recruited from the community or they may be approached by collaborating clinicians or research team members (see recruitment plans) to explore potential participant's interest in taking part in a research study. Those who are interested will receive a telephone call from research staff to conduct a telephone screen. Those who pass the phone screen will receive an appointment to come to the research location to review and sign the informed consent form for screening purposes and to complete baseline diagnostic assessment screen, blood draw to test for CRP level, Hepatitis B and C, HIV, and rheumatoid arthritis, and will also complete an EKG to determine eligibility. Those who are eligible will return for a baseline visit and will review and sign another informed consent form for participation in the full protocol. Once fully consented, participants will undergo a series of visits to conduct multiple assessments which will include:

- (1) Psychological and Neuropsychological Tests at baseline and week 6; Open Label at week 6;
- (2) Medical Examination;
- (4) 3-4 Blood Collections (blood draw at screening, blood draw at baseline, blood draw at week 2 for liver function and hematocrit assessment, and one at Week 6) for those who enter the open-label phase they will receive an additional 2 blood draws (one at Open Label Week 2 to assess for liver function and hematocrit levels, and one at Open Label Week 6). All participants will be asked if willing to participate in additional blood collection for immune profiling.
- (5) 2-3 MRIs, one at baseline, one at week 6, and one at open-label week 6; the baseline scan will occur before treatment begins;
- (6) 2-3 fMRI (one at baseline which will occur during the same baseline MRI session, one at Week 6, and one at open-label week 6);
- (7) Optional Nutrition Assessment. Participants will be asked to do a 24-hour dietary recall. The food recall will also be collected using the Nutrition Data System for Research (NDSR). Participants are guided through a multiphase interview where they are guided to recall all the food they ate in the preceding 24 hours.

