#### **5.4 Blood draws**

During the screening visit, all participants will have a blood draw to test for CRP levels to stratify the participants accordingly in High CRP and Low CRP groups. Participants will also have a blood sample drawn at the end of the screening visit to test immediately for Hepatitis B and C, HIV, autoimmune diseases (double-stranded DNA test), and rheumatoid factor; as well as to use in later analyses of inflammatory markers. Participants will have a blood sample drawn (approximately 16.5mL) at the screening visit, approximately 40 mL at the baseline visit, approximately 40 mL at the end of the study, 40 mL at the end of the open label phase. Blood samples will be used for doing tests for inflammatory markers and for measuring levels of Interleukin-6, Interleukin-10, TNF-alpha, and C-reactive protein. We will look at immunological markers by two methods; luminex and flow cytometry. The Luminex assay measures soluble proteins in the sera. Molecules such as IL-6 and TNF-alpha, MIP1-alpha, IFN-alpha, CRP will be assessed. We will include or alter molecules in the luminex assay based on the most recent literature as we near the end of sample collection. Flow cytometry will also be utilized. Flow cytometry will be used to measure the status of T cells which are important in suppressing such conditions as infectious disease and cancer. We will develop a series of markers that define the memory and naive phenotype of T cells along with their activation status and functionality. We will also assess additional cell subsets such as NK and macrophages. Molecules that will be assessed include but are not limited to; CD3, CD4, CD8, CD45RO, CD27, CCR7, CD69, CD33, CD68, CD56, CD16, CD38 and HLADR and CD11c -monocytes. Some blood will be retained and banked for future research. Additional blood is being collected for ex vivo isolation of human peripheral blood mononuclear cells (PMBC), which is another assessment of inflammation levels. This additional blood draw will be optional and offered to all depressed participants.

Participants will give blood for a liver-function test and for hematocrit levels to test for GI bleeding. Participants may also have 24-hour ambulatory blood-pressure monitoring. Participants may wear a cuff for 24 hours that is set to automatically take blood pressure every 15 minutes during the day and every 30 minutes during the night.

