#### **5.5 Gastrointestinal Safety**

At the beginning of the study, GI/bleeding risks will be examined. Hematocrit levels will be tested in blood samples to assess this risk at baseline, and at week 2.

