#### **10.1.6 Celecoxib**

Celecoxib has been associated with an increased risk of cardiovascular events in people with cardiovascular disease (Celecoxib package insert). Side effects include nausea, diarrhea, gas, cold symptoms, sore throat, lack of energy, loss of appetite, fever, rash, back pain, and flu-like symptoms, among others. Participants would be instructed to contact study members if severe,

CONFIDENTIAL

serious, or persisting side effects occur. There is a rare risk of stroke or heart attack; however these very serious side effects are greatest risk for those with current clinically significant cardiac disease, and we are excluding these people (clinically significant cardiovascular disease usually includes one or more of the following: cardiac surgery or myocardial infarction within the last 4 weeks; unstable angina; acute decompensated congestive heart failure or class IV heart failure; current significant cardiac arrhythmia or conduction disturbance, particularly those resulting in ventricular fibrillation, or causing syncope or near syncope; uncontrolled high blood pressure; QTc greater than 450msec (by history for subjects with cardiac disease); documented prior stroke; clinically significant abnormalities on EKG.) Celecoxib also has increased risk for gastrointestinal bleeding and hepatic impairment. We will exclude those with current ulcer disease or GI bleeding as well as those with liver function impairment (as determined by a liver function test prior to entry into the study). We are excluding clinically significant cardiovascular disease for the past 6 months.

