## 12 Appendix

### 12.1 Study Flow-Chart

Procedures conducted with all participants				
Procedure	Phone Screen	In-person Screen	Baseline	Week 6
Informed Consent		X (Initial screening consent)	X (Full study consent)	X
Verbal Consent	X			
Screen, History (include GI/bleeding risks)	X			X
Screen, History, SCID, MADRS, HAMD, CGI, MOCA		X		
EKG		X		X
PE , Laboratory tests, including IL-6, IL-10, CBC with diff;		X	X	X
MRI; structural and functional			X	X
Lifetime depression, PSS, LES score			X	
Framingham VRF, CIRS-G, QOL		X		X
Neuropsychological tests (COWA, Trails A & B, WLMT, Digits Forward, Digits Backward, Digits Ascending, MMSE, Logical Memory, Digit Symbol, Benton Visual Retention, Shipley Vocabulary, Boston Naming, CogState)			X	X

\*.

CONFIDENTIAL

This material is the property of the University of Pennsylvania.

Additional procedures conducted with depressed participants initially randomized to celecoxib:					
Procedure	Study Visits				
	Baseline	Wk 1	Wk 2	Wk 4	Wk 6
Concomitant Medications	X	X	X	X	X
Drug Dispensed Escitalopram + celecoxib or escitalopram + placebo (weeks 0-6)	X	X	X	X	X
Psychiatrist evaluation, depression scales, Vital Signs (including optional urine samples at baseline, week 1 or 2, and 6; triplicate in-office BP weekly and monitor GI-pain/bleeding for safety ),AEs, SAEs	X	X	X	X	X
PE (Lab tests including IL-6, IL-10, CBC with diff)	X	X	X	X	X
Liver function test & GI/bleeding risks	X		X		
Actigraphy (1 consecutive day minimum, optional longer),		X	X	X	
Optional Stool Sample	X		X		X
Optional Saliva samples	X	X	X	X	X
Safety (ABPM, FOBT and/or hematocrit levels)	X		X		
Safety (24-hour dietary recall, optional counseling on sodium-deplete diet)	X	X			

CONFIDENTIAL

This material is the property of the University of Pennsylvania.

	Additional procedures conducted with depressed participants initially randomized to placebo:									
	Procedure			Phase 1			Open Label Phase			
	Baseline	Wk 1	Wk 2	Wk 4	Wk 6	Wk 1	Wk 2	Wk 4	Wk 6	
Concomitant Medications	X									
Drug Dispensed Escitalopram + celecoxib or escitalopram + placebo (weeks 0-6) (Open label- Escitalopram + celecoxib)	X	X	X	X	X	X	X	X	X	
Psychiatric evaluation, depression scales, Vital Signs (including optional urine samples at baseline, week 1 or 2, and 6; triplicate in-office BP weekly and monitor GI-pain/bleeding for safety ),AEs, SAEs	X	X	X	X	X	X	X	X	X	
Liver function test & GI/bleeding risks	X		X				X			
Actigraphy	X	X	X	X	X	X	X	X	X	
Optional Saliva samples	X	X	X	X	X	X	X	X	X	

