Safety (ABPM, FOBT and/or hematocrit levels)	X		X				X			
Safety (24-hour dietary recall, optional counseling on sodium-deplete diet)	X	X				X	X			

CONFIDENTIAL

This material is the property of the University of Pennsylvania.

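### The end-of-study hepatic panel and hematocrit promised for celecoxib safety are not carried into the schedule: neither is set at open-label week 6, and the hepatic panel at week 6 is left to interpretation

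*Combined protocol and SAP*

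**What the plan says.** All references are to the combined protocol and SAP.

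- **Promise.** Section 10.5.1, Gastrointestinal Bleeding Risk of Celecoxib (the second section with that number), sets three time points: "hepatic function panel and hematocrit blood testing before entering the study, during week 1 or 2, and at the end of the study".
- **Reason for testing.** Section 10.1.6 states: "Celecoxib also has increased risk for gastrointestinal bleeding and hepatic impairment".
- **Procedures list.** Section 5.2 assigns liver function and hematocrit to the week 2 draw and lists a week 6 draw without a safety test. For the open-label phase it gives "one at Open Label Week 2 to assess for liver function and hematocrit levels, and one at Open Label Week 6".
- **GI safety section.** Section 5.5 says "Hematocrit levels will be tested in blood samples to assess this risk at baseline, and at week 2". It does not mention liver tests.
- **Flow chart (12.1).** The row "Liver function test & GI/bleeding risks" is ticked at baseline and week 2 for both randomized groups, and at open-label week 2. The row beginning "Safety (ABPM, FOBT and/or hematocrit levels" has the same pattern. Separately, the table for all participants has a row "PE , Laboratory tests, including IL-6, IL-10, CBC with diff", ticked at the in-person screen, baseline and week 6.
- **Blood volumes.** Section 5.4 plans about 40 mL at the end of the study and 40 mL at the end of the open-label phase.

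**The concern.** The protocol offers end-of-study laboratory testing as part of its mitigation for two named celecoxib risks. The flow chart is the working schedule, and its dedicated rows do not contain that time point. A site that follows those rows could leave out a test that the risk section says is done.

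Two things are at stake. First, section 7.6.1.3 makes laboratory blood chemistry part of the DSMB's safety data. Without a closing panel, that chemistry may hold no liver result from the later weeks of celecoxib exposure. Second, participants on placebo who do not remit start celecoxib after week 6. A normal liver test is an entry criterion (2.8), yet the most recent explicitly scheduled result at that moment is from week 2.

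**Working it through.** The plan gives no figure to reproduce. The check is to place each scheduled test under its visit and compare it with the promise.

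| Visit | Blood drawn? | Hepatic panel | Hematocrit |
|---|---|---|---|
| Baseline | Yes | Ticked, liver row | Ticked, hematocrit row and blood count |
| Week 2 | Yes (5.2) | Ticked, liver row | Ticked, hematocrit row |
| Week 6 | Yes (5.2, 5.4) | Liver row blank; possible only through the open-ended laboratory row | Covered by the blood count |
| Open-label week 2 | Yes (5.2) | Ticked, liver row | Ticked, hematocrit row |
| Open-label week 6 | Yes (5.2, 5.4) | Liver row blank; no laboratory row in these columns | Hematocrit row blank; no blood-count row in these columns |

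**Randomized phase, hematocrit.** A complete blood count contains a hematocrit. It is ticked at week 6 for everyone, and the celecoxib table also ticks it at weeks 1, 2 and 4. The promise is met.

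**Randomized phase, hepatic panel.** The dedicated row stops at week 2. The only other place for it at week 6 is the all-participants laboratory row, whose list is introduced as non-exhaustive and does not name liver function.

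**Open-label phase.** For a participant who enters this phase, the end of the study is open-label week 6. Both dedicated rows stop at open-label week 2. The table has no laboratory or blood-count row, and section 5.2 names no safety test for the last draw. Section 5.2 also says that entrants repeat the procedures of the first phase. That explicitly carries over at most a blood count, because the first phase does not explicitly schedule a hepatic panel at week 6.

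**Size.** One celecoxib course lasts 6 weeks, or 42 days.

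- Days after the last explicitly scheduled test: 42 − 14 = 28.
- Share of the course: 28 / 42 = 0.67.
- In the open-label phase this share applies to both tests. In the randomized celecoxib arm it applies to the hepatic panel only, and only if the open-ended row is read as not including it.
- Age of the last explicitly scheduled liver result when a placebo non-remitter starts celecoxib: 6 − 2 = 4 weeks.

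**The case against.** The best defence concerns week 6 of the randomized phase. The liver row stands in tables of additional procedures, so a blank there does not cancel a test listed in the table for all participants. Section 2.8 requires a normal liver test from everyone, controls included, and controls have only the all-participants table, which has no liver row. Their screening liver test must therefore sit in the open-ended laboratory row, and that row is also ticked at week 6. The row likewise omits the screening HIV, hepatitis and rheumatoid tests, so it is plainly not complete. With the promise in section 10.5.1, a week 6 hepatic panel is a fair reading. This stands: the week 6 liver gap is an ambiguity, not a demonstrated omission. The defence does not reach open-label week 6, where there is no such row.

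Three stronger readings might be inferred, and the documents do not support them.

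- *The end-of-phase blood is reserved for inflammatory markers.* Section 5.4 does say "40 mL at the end of the open label phase. Blood samples will be used for doing tests for inflammatory markers", but that statement also covers the screening and baseline samples. A later sentence in the same section provides for liver-function and hematocrit testing without giving a time.
- *Only the EKG and cardiac risk are rechecked before open-label celecoxib.* Section 10.4 describes that cardiac check, but the flow chart also repeats history with bleeding risk, physical examination, blood count and illness ratings at week 6.
- *Late hepatic or bleeding harm would go unnoticed.* GI pain and bleeding checks, adverse-event questioning (7.2) and medical-monitor review (7.6.1.2) continue throughout. The gap is in laboratory cover.

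**Conclusion.** The inconsistency is real but narrow. It is firm at open-label week 6, where neither promised test is explicitly scheduled although blood is drawn. It is softer at week 6 of the randomized phase, where hematocrit is covered and the hepatic panel depends on how one row is read.

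The laboratory gap is the last 28 of 42 days (67%) of the open-label course for both tests, and possibly the same share of the randomized celecoxib course for the hepatic panel.

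Expected harm is low. Section 1.2 reports no evidence of more GI or cardiovascular events after 6 weeks. Section 10.5.1 cites an upper-GI rate ratio of 1.32 (99% CI 0.45 to 3.86) at 800 mg per day, twice the dose used here. Section 10.5.3 describes profiles like placebo on co-administration, though in small studies. The example monitoring form (12.3) offers a close-out option for laboratory review without naming tests, which suggests that closing labs were intended.

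This is a minor consistency correction. It assumes that the flow-chart ticks belong to the visit columns in the order printed, and that the end of the study for an open-label entrant is open-label week 6.

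**What to change.** 1. In the flow chart, tick a hepatic panel at week 6 for all depressed participants. It serves as the closing test for the celecoxib arm and as the pre-celecoxib result for placebo non-remitters. Doing it in both arms protects the blind.
2. Tick a hepatic panel and a blood count (or hematocrit) at open-label week 6.
3. Align sections 5.2 and 5.5 with section 10.5.1, so that the safety tests are named at the end-of-phase draws.

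If the sponsor did not intend closing tests, section 10.5.1 should be changed instead, with a reason. Either way the text and the schedule must agree.

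Both draws already take place, so no visit or needle stick is added. The cost is laboratory fees, a few text edits and investigator review of a few mildly abnormal results.

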## 12 Appendix

### 12.1 Study Flow-Chart

Procedures conducted with all participants				
Procedure	Phone Screen	In-person Screen	Baseline	Week 6
Informed Consent		X (Initial screening consent)	X (Full study consent)	X
Verbal Consent	X			
Screen, History (include GI/bleeding risks)	X			X
Screen, History, SCID, MADRS, HAMD, CGI, MOCA		X		
EKG		X		X
PE , Laboratory tests, including IL-6, IL-10, CBC with diff;		X	X	X
MRI; structural and functional			X	X
Lifetime depression, PSS, LES score			X	
Framingham VRF, CIRS-G, QOL		X		X
Neuropsychological tests (COWA, Trails A & B, WLMT, Digits Forward, Digits Backward, Digits Ascending, MMSE, Logical Memory, Digit Symbol, Benton Visual Retention, Shipley Vocabulary, Boston Naming, CogState)			X	X

\*.

CONFIDENTIAL

This material is the property of the University of Pennsylvania.

Additional procedures conducted with depressed participants initially randomized to celecoxib:					
Procedure	Study Visits				
	Baseline	Wk 1	Wk 2	Wk 4	Wk 6
Concomitant Medications	X	X	X	X	X
Drug Dispensed Escitalopram + celecoxib or escitalopram + placebo (weeks 0-6)	X	X	X	X	X
Psychiatrist evaluation, depression scales, Vital Signs (including optional urine samples at baseline, week 1 or 2, and 6; triplicate in-office BP weekly and monitor GI-pain/bleeding for safety ),AEs, SAEs	X	X	X	X	X
PE (Lab tests including IL-6, IL-10, CBC with diff)	X	X	X	X	X
Liver function test & GI/bleeding risks	X		X		
Actigraphy (1 consecutive day minimum, optional longer),		X	X	X	
Optional Stool Sample	X		X		X
Optional Saliva samples	X	X	X	X	X
Safety (ABPM, FOBT and/or hematocrit levels)	X		X		
Safety (24-hour dietary recall, optional counseling on sodium-deplete diet)	X	X			

CONFIDENTIAL

This material is the property of the University of Pennsylvania.

	Additional procedures conducted with depressed participants initially randomized to placebo:									
	Procedure			Phase 1			Open Label Phase			
	Baseline	Wk 1	Wk 2	Wk 4	Wk 6	Wk 1	Wk 2	Wk 4	Wk 6	
Concomitant Medications	X									
Drug Dispensed Escitalopram + celecoxib or escitalopram + placebo (weeks 0-6) (Open label- Escitalopram + celecoxib)	X	X	X	X	X	X	X	X	X	
Psychiatric evaluation, depression scales, Vital Signs (including optional urine samples at baseline, week 1 or 2, and 6; triplicate in-office BP weekly and monitor GI-pain/bleeding for safety ),AEs, SAEs	X	X	X	X	X	X	X	X	X	
Liver function test & GI/bleeding risks	X		X				X			
Actigraphy	X	X	X	X	X	X	X	X	X	
Optional Saliva samples	X	X	X	X	X	X	X	X	X	
Safety (ABPM, FOBT and/or hematocrit levels)	X		X				X			
Safety (24-hour dietary recall, optional counseling on sodium-deplete diet)	X	X				X	X			

CONFIDENTIAL

This material is the property of the University of Pennsylvania.

## 12.2 Diary Recall Form (example)

### To The Patient

The portable automatic blood pressure unit that you are wearing measures and records your blood pressure and heart rate at predetermined intervals. Be sure that the monitor is comfortably positioned before you leave the office, then go about your normal daily activities. The heart rate data should be used for reference only, not as clinical diagnostic data.

To obtain maximum information from the monitor, it is important that you record in this diary the initial TIME when the cuff inflates, the ACTIVITY in which you are involved when the reading is taken and the time at which you take your MEDICATIONS. It is unnecessary to list redundant activities and the time of day when the cuff inflates; just list the activities when they change (i.e., work to leisure activity). In addition, if symptoms occur between readings, push the START/STOP button on the monitor and an additional reading will be taken. Readings will then continue on a normal cycle. Be sure to describe the symptoms in the diary. Should you wish to abort a reading in progress, simply push the START/STOP button.

### Important Notes

DO	once the tone sounds, avoid unnecessary movement while the blood pressure reading is being recorded. Try to keep your arm still.
DO NOT	remove the blood pressure monitor from the carrying case.
DO NOT	flip the ON/OFF switch as this will turn the blood pressure monitor off. Turn the machine off only in emergencies.
DO NOT	get the monitor wet; however, should the monitor get wet, there is no electrical shock hazard from the monitor.
DO NOT	worry if the blood pressure monitor cannot take a blood pressure reading every time it cycles. If it can't take a reading, remain still and the monitor will make one more attempt to measure your blood pressure in 60 seconds. (If a reading cannot be recorded, an event code will appear on the display.)

AMBULATORY BLOOD PRESSURE MONITOR

